# 6.2 Outcomes

Outcome	Timing of measurement	Method of measurement	Objective	
Primary outcome	Primary outcome			
Caries experience (measured at dentinal level) at 24 months post- randomisation in any tooth which was caries free or unerupted at baseline	Baseline and 24 months (+/-3 months post randomisation).	Dental status examination to national standards as used in UK Dental Epidemiology Surveys of Child Dental Health	1, 8, 10, 11	
Secondary outcome(s)				
Number of teeth (caries free or unerupted at baseline) with caries experience into dentine 24 months post-randomisation.	Baseline and 24 months (+/-3 months post randomisation).	Dental status examination to national standards as used in UK Dental Epidemiology Surveys of Child Dental Health	2, 8	

 
Parent reported attitudes to child oral health behaviours (seven subscales)
 
Parental efficacy in relation to child toothbrushing
 
Importance and intention to brush child's teeth
 
Parental efficacy in relation to controlling child sugar snacking
 
	Baseline, 12 months and 24 months (+/- 3 months post randomisation).	Parent reported Oral Health Behaviours and Regret/Relief Questionnaire (OHB-RRQ)	2,8, 10, 11	

 
Importance and intention to control child sugar snacking
 
Perceived seriousness of tooth decay in children
 
Chance control – decay occurs by chance
 
Regret/Relief regarding child oral health behaviours
 
			

 
Parent reported child oral health behaviours (four measures)
 
Level of toothbrushing
 
Sweets consumption
 
Sugary drinks consumption
 
Dental attendance
 
	Baseline, 12 months and 24 months (+/- 3 months post randomisation).	Parent reported Oral Health Behaviours and Regret/Relief Questionnaire (OHB-RRQ)	2, 8
Episodes of dental pain	12 months and 24 months (+/- 3 months post randomisation).	From child dental treatment records of episodes of dental pain.	2
Number of filled teeth (caries free or unerupted at baseline) 24 months post randomisation	Baseline and 24 months (+/-3 months post randomisation).	Dental status examination to national standards as used in UK Dental Epidemiology Surveys of Child	2
Number of extracted teeth (caries free or unerupted at baseline) 24 months post randomisation	Baseline and 24 months (+/- 3 months post randomisation).	Dental status examination to national standards as used in UK Dental Epidemiology Surveys of Child	2
Economic outcomes			
Health related quality of life	Baseline, 12 months and 24 months (+/- 3 months post randomisation).	EQ-5D-Y Proxy Version 1; EQ- 5D-Y Interviewer Administered Proxy Version 1; EQ-5D-Y Proxy REDcap, general dental practice records and administrative records	3
Oral health related quality of life	Baseline, 12 months and 24 months (+/- 3 months post randomisation).	Parental-Caregiver Perceptions Questionnaire (Marshman et al., 2005)	3
Costs of treatment	24 months, 10 years	Dental records of index child and siblings from administrative* records	3,4
SWAT outcomes			
Attendance for a dental checkup	During 18-month recruitment phase	Dental attendance records	6

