#### 6.1.2 Secondary objectives:

2. To evaluate the effect of delivering DR-BNI and usual care two years after DR-BNI intervention on: number of teeth with caries experience, episodes of dental pain, number of fillings, extractions, reported child oral health behaviours (sugar control, tooth brushing, dental attendance), and parental attitudes towards these behaviours.

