# 8.1 Inclusion Criteria

Patients eligible for the trial must comply with all of the following at baseline:

- Child has at least one carious lesion into dentine
- Aged ≥3 years and <8 years at the time of randomisation
- Child is receiving NHS dental care
- The intervention can be received in a comprehensible way by the child's parent/primary caregiver
- Written and informed consent obtained from child's parent/primary caregiver and agreement to comply with the requirements of the study

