# 8.2 **Exclusion Criteria**

Any patient meeting any of the criteria listed below at baseline will be excluded from study participation:

- Child presents with advanced caries that require referral for extractions
- Child presents with only arrested carious lesions into dentine in primary teeth [arrested as defined within national epidemiological criteria].
- Child is living in the same household as someone already recruited to the CHOICE Trial.

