### 10.8.3 Efficacy Assessments

The primary outcome, the efficacy assessment, is measured 24 months post-randomisation (+/- 3 months), and is the development of caries in any tooth which was caries free or unerupted at baseline. Caries is measured at the dentinal level of involvement (Pitts et al., 1997). Children will be examined supine with a single-use plane mouth mirror, and teeth will be illuminated by a portable Daray light of 2,000 lux. The presence of upper anterior buccal plaque will be recorded as an indicator of oral cleanliness. Teeth will be examined for untreated caries into dentine, restorations, and fissure sealants. (Pitts et al., 1997) Cotton wool rolls will be used to dry teeth, and probes will be available to remove debris and to check the integrity of restorations and the presence of sealants. Examining procedures are those set by the national dental epidemiology programme under which children are examined in school using mobile equipment (Public Health England, 2021). Assessments will be conducted in the child's dental practice, where possible, or in the child's school or if requested by parent, at the child's home. All dental assessments will be blind to group assignment. Organisation of the timetable for the clinical assessments including contacting practices, schools and families will be undertaken by the CHOICE central research team based at Queen's University Belfast.

All dental treatment that is provided will be recorded by the participants' general dental practitioner (GDP) during the trial period. At the time of final assessment, dental records will be examined of the trial participants by the GDP to capture all the dental treatment and reported dental pain. Hospital records of dental extractions will also be recorded. Where consent has been provided, administrative records will be used for the study period for any siblings (aged up to 11 years on study entry) residing with the participant and attending the same dental practice to assess their dental treatment.

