## 13.2 Sample Size

## 13.2.1 Sample Size Calculation

In the clinical trial evaluating the DR-BNI technology in secondary care, the Dental RECUR trial, 62% of children in the control group developed new caries, compared to 44% in the test group, a difference of 18 percentage points. An inclusion criterion for that trial was that the child was scheduled to have at least one primary tooth extracted. The children in the sample achieved had a median of 5 teeth extracted. In addition to the high levels of dental caries experience, the children were aged between 5 and 7 years at recruitment. The children eligible to join the CHOICE trial will have at least one decayed tooth but we will exclude those whose disease is so advanced that they require dental extractions. This is a critical distinction, as one of the objectives of the CHOICE trial is to determine whether earlier intervention in the disease process using DR-BNI can reduce the number of children needing dental extractions; as well as reduce the number having restorations for caries, so further reducing the cost of care to the NHS. The CHOICE trial will also include children at a younger age, from 3 to 7 years, rather than from 5 to 7 years. Therefore, there is potential for a smaller difference to be clinically important achieving a longer-term benefit. These differences in the sample composition mean that it is important to power the trial to detect a smaller difference than found in the RECUR trial, as this difference will be clinically important. Therefore, the CHOICE trial has been powered to detect a clinically significant difference of 12 percentage points.

To give 90% power, with  $\alpha$ =0.05, requires 363 participants per group. Allowing for 20% loss to follow-up, we will aim to recruit 454 participants per group, 908 in total. We will provide each of the 4 regions with a recruitment target of 227. Each region aims to recruit 10 dental practices, resulting in an achieved sample size target per practice of 22-23 patients over an 18-month recruitment period.

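### The only extraction outcome leaves out teeth already carious at baseline, so as defined it does not measure how many children need extractions, which Section 13.2.1 names as an objective

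*Protocol*

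**What the plan says.** **The aim.** Section 13.2.1 explains why children with disease advanced enough to need extraction are not enrolled, and in doing so says that one objective is to "determine whether earlier intervention in the disease process using DR-BNI can reduce the number of children needing dental extractions". That is a statement about children, for any tooth. Objective 2 in Section 6.1.2 evaluates "number of teeth with caries experience, episodes of dental pain, number of fillings, extractions, reported child oral health behaviours", and it too sets no condition on which extracted teeth count.

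**The outcome.** Section 6.2 (and the overview in Section 3) has one extraction outcome: "Number of extracted teeth (caries free or unerupted at baseline) 24 months post randomisation". Its stated method is "Dental status examination to national standards as used in UK Dental Epidemiology Surveys of Child", at baseline and 24 months. Section 13.6 compares numbers of extractions by Poisson regression adjusted for site and baseline caries.

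**The population.** Section 8.1 requires that "Child has at least one carious lesion into dentine". Section 8.2 excludes a child if "Child presents with advanced caries that require referral for extractions".

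**Other extraction data.** The schedule in Section 10.8 has the dentist abstract treatment from practice records at 12 and 24 months. Section 10.8.3 adds: "Hospital records of dental extractions will also be recorded". The only use the protocol states for extraction data from these sources is in the health economic analysis, chiefly costing (Sections 10.8.8 and 13.7).

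**The concern.** The aim and the outcome differ in two ways. The unit differs: the aim is about children, while the outcome counts teeth. The teeth at risk also differ: the aim covers any tooth, while the outcome drops every tooth that was already carious. The second difference matters more. The baseline lesion is what makes a child eligible, and if it progresses to extraction during follow-up, including extraction in hospital, the extraction outcome does not register it.

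The trial could therefore report its extraction result and still leave readers without an estimate for the question posed in Section 13.2.1. If such an estimate were produced later from the records, it would be a post-hoc outcome.

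**Working it through.** The argument is about definition. Arithmetic only illustrates its size.

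**1. The plan's own figure.** Section 13.2.1 gives 363 per group for a 12-point difference at 90% power and α = 0.05. No control rate for this trial is stated. With a two-sided test and 56% v 44% (assumed), p̄ = 0.50:

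n = [1.96·√(2·0.5·0.5) + 1.2816·√(0.56·0.44 + 0.44·0.56)]² / 0.12² = (1.386 + 0.900)² / 0.0144 ≈ 363.

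55% v 43% also gives 363, and 62% v 50% gives 358. Then 363/0.8 = 454 per group and 908 in total. The sample size reproduces and is not in dispute. It concerns the primary outcome only.

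**2. What each child can score.** Three kinds of child with an extraction during follow-up:

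| Teeth extracted by 24 months | Needed an extraction (13.2.1) | Extraction count (6.2) |
|---|---|---|
| Only teeth carious at baseline | Yes | 0 |
| Only teeth sound or unerupted at baseline | Yes | 1 or more |
| Both kinds | Yes | Only the second kind counted |

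The first row is misread by the count, and would be misread by a yes/no version of it too. Section 8.1 guarantees that every child has a tooth through which the first row can occur.

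**3. Illustration of lost information (assumed inputs).** Let p be the control-group risk of any extraction, and s the share of children with an extraction who lost only baseline-carious teeth. Neither is in the protocol. To compare like with like, use yes/no outcomes, 363 analysed per group and the same risk ratio (RR) for all teeth. Then p₁ = p(1−s), p₂ = RR·p(1−s), and

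power = Φ{ [|p₁−p₂| − 1.96·√(2p̄(1−p̄)/n)] / √([p₁(1−p₁)+p₂(1−p₂)]/n) }.

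For p = 0.20, s = 0 and RR = 0.6: p₁ = 0.20, p₂ = 0.12, p̄ = 0.16, so power = Φ[(0.08 − 1.96·0.0272)/0.0270] ≈ Φ(0.99) ≈ 84%.

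| Control risk p (RR 0.6) | all teeth count (s = 0) | s = 25% | s = 50% | s = 75% |
|---|---|---|---|---|
| 10% | 51.1% | 39.8% | 27.9% | 15.9% |
| 20% | 83.8% | 70.2% | 51.1% | 27.9% |
| 30% | 96.7% | 88.6% | 70.2% | 39.8% |

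With RR 0.7 and p = 20%, the row is 57.6%, 44.3%, 30.5% and 16.9%.

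**4. Illustration of a different answer.** Suppose instead that the intervention acts only on teeth sound at baseline, with RR 0.70 there and 1 for the rest. The child-level any-tooth ratio is s·1 + (1−s)·0.70, which is 0.775, 0.85 and 0.925 at s = 25%, 50% and 75%. The restricted outcome would show 0.70 and so overstate the effect on children needing extractions. The direction of the discrepancy therefore depends on where the intervention acts, which the protocol cannot settle in advance.

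**The case against.** **The restriction is coherent.** The primary outcome, the carious-teeth count and the filled-teeth count use the same base of sound or unerupted teeth. That isolates new disease, which is what a preventive conversation targets. Teeth decayed before randomisation may need treatment that prevention cannot avert. This stands as a reason to keep the restricted count, but it does not make that count answer the Section 13.2.1 question.

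**The child-level wording is only rationale.** It sits in the sample-size section, and the formal objectives contain no child-level extraction objective. That is fair, and rewording Section 13.2.1 would remove much of the contradiction. But the sentence calls it an objective, objective 2 is also unrestricted, and rewording alone would leave the question unanswered when the data for it are being gathered.

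**Stronger readings that the documents do not support:**

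- A reader might infer that the trial will be unable to say anything about extractions. The records in Sections 10.8 and 10.8.3 would allow it. What is missing is a prespecified clinical outcome. The SAP was not available and might add a supporting analysis, but the protocol itself fixes the outcome definition.
- A reader might infer that the count mixes shed and extracted primary teeth. Section 10.4.1 trains examiners to assess why teeth are absent and applies the same criteria at 24 months. Some misclassification may remain, but the document gives no ground for more than that.
- A reader might infer that most extractions will come from baseline-carious teeth. The protocol gives no such share, and Section 8.2 removes children already needing referral for extractions.
- A reader might infer that Section 6.2 ignores records altogether. Dental pain and treatment costs are taken from records; only the extraction row is not.
- A reader might infer that the primary outcome needs a further sensitivity analysis. Nothing here makes that case.

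**Conclusion.** The point holds as a mismatch between stated aim and outcome definition, and that conclusion needs no outside figure. The restricted count informs part of the aim, namely extraction after new caries, and is silent on the rest. Its numerical size is unknown. The power and risk-ratio figures rest on assumed extraction risks of 10% to 30%, assumed shares of 25% to 75%, and a yes/no comparison in place of the planned Poisson count. They show that the consequence could be anything from modest to large. The primary outcome, its analysis and the sample size are not touched. This is a secondary-outcome matter that should be settled before any comparative analysis.

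**What to change.** 1. Keep the count of extracted teeth that were sound or unerupted at baseline.
2. Add a prespecified secondary outcome at child level: any extraction for caries, in any tooth, from randomisation to 24 months, taken from practice and hospital records. Report hospital extractions separately as well.
3. Analyse it by logistic regression adjusted for site and baseline caries, as for the primary outcome.
4. Align Sections 6.1.2, 6.2 (with the Section 3 overview), 13.2.1 and 13.6, so that the aim, the outcome and the analysis refer to the same quantity.
5. Confirm that the eCRF captures tooth, date and reason for each extraction. The protocol does not say so.

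The cost is mainly wording in the protocol and SAP, plus possibly an eCRF field. No visit or data source is added. There is one small drawback: the records are kept by practices that know the allocation (Section 7.2), so the outcome should be labelled as unblinded. The same already applies to the dental pain outcome, which Section 6.2 takes from treatment records.

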#### CHOICE Protocol V2.0, 08.02.2024 Based on protocol template v1.0 11/10/2019

Recruitment into the CHOICE	During 18-month	Recruitment data	6
Qualitative outcomes			
Fidelity to the DR-BNI	Intervention visit	Audio recordings of the DR-BNI Intervention/fidelity checklist	
Number and type of goals chosen; behaviour techniques used	Intervention visit	Audio recordings of the DR-BNI intervention	7
Facilitators and barriers to recruitment of the target population	18-24 months from the start of the trial	Qualitative interviews	5
Implementation of DR-BNI	24-36 months from the start of the trial	Qualitative interviews	9
ENCOURAGE outcomes			
Salivary levels of lactic acid	Randomisation visit (Baseline) and 6 months (+/-1 month post randomisation).	Salivary metabolomics	12
Salivary levels of pyruvic acid, citric acid, 2-ketoglutamic acid, succinic acid, malic acid and fumaric acid	Randomisation visit (Baseline) and 6 months (+/-1 month post randomisation).	Salivary metabolomics	13
Bacterial and fungal microbiome	Randomisation visit (Baseline) and 6 months (+/-1 month post randomisation).	Internal Transcribed 14 Spacer (ITS) ribosomal RNA (rRNA) for identification of fungi and 16S sequencing for identification of bacteria in saliva samples	

\*Administrative data sources include NHS Digital, NHS Business Services Authority (BSA), Business Services Organisation (BSO), Patient Administration System (PAS) or their successors.

# 7 TRIAL DESIGN

CHOICE aims to compare the clinical effectiveness and cost-effectiveness of the behavioural intervention DR-BNI in addition to usual care in 3–7-year-old children versus usual care alone. CHOICE is designed as a two-arm randomised controlled trial (RCT) and is an outcome assessor-blinded trial.

The trial will be conducted in general dental practices in four regions of the UK: The North West; East of England; Yorkshire and the Humber; and in Northern Ireland.

The primary outcome, measured 24 months (+/- 3 months) post randomisation, is the development of caries in any tooth which was caries free or unerupted at baseline.

The design includes an internal pilot to assess recruitment of practices and participants with pre-determined progression criteria to the main trial.

# 7.1 Blinding

Where possible, final dental assessments at 24 months (+/- 3) will be undertaken by a single, trained examiner who will be blind to child's group allocation. If a single examiner is not feasible, for example due to rapid recruitment, then a reserve plan will be used that will include a team of trained assessors, to undertake the final dental assessments. The examiner/s will be independent to the general dental practices and will not have access to documentation containing trial allocation.

# 7.2 Who is blinded

As mentioned in section 7.1, a blinded outcome assessor will complete the final dental assessment at 24 months (the 24-month final assessment). Dental practice staff at all participating practices, LCTC staff and participants will be aware of treatment allocation.

# 7.3 Trial Setting

Participants will be identified and recruited from up to 40 general dental practices in the UK; approximately 10 per region in: The North West of England; East of England; Yorkshire and the Humber; and in Northern Ireland. Follow up will occur within the same dental practices providing usual care for these patients.

#### 7.3.1 Selection of Participating Sites

Criteria for the selection of centres will be determined by the Trial Management Group and will be described in a separate document 'CHOICE Site Suitability Assessment Form' maintained in the Trial Master File (TMF).

Sites fulfilling the trial-specific criteria will be selected to be recruitment centres for the CHOICE trial and will be opened to recruitment upon successful completion of all global (e.g. REC) and study-specific conditions (e.g. site personnel training requirements) and once all necessary documents have been returned to the LCTC. Initiation of sites will be undertaken in compliance with LCTC internal processes. Conditions and documentation required will be detailed on a LCTC Green Light Checklist maintained in the TMF and must be fully completed prior to opening sites to recruitment.

#### 7.3.2 Selection of Principal Investigators

Principal Investigators will be required to demonstrate equipoise and commitment during early stage feasibility assessment. All Investigators will have the particular dental expertise necessary to conduct the study in accordance with the protocol and all regulatory and ethical requirements. Investigators will also be required to provide evidence of GCP training dated within 3 years at site initiation. Written agreement to conduct research as such will be obtained prior to site initiation.

A suitable Co-Investigator should be identified (where possible) at each site to deputise in case of PI absence.

# 8 ELIGIBILITY CRITERIA

The CHOICE trial aims to recruit 908 patients based on sample size calculations described in Section 13.2.1. Written, informed consent must be provided for all patients before any study procedures occur (see Section 10.2 for more information regarding informed consent processes) and they must meet all eligibility criteria as described below.

# 8.1 Inclusion Criteria

Patients eligible for the trial must comply with all of the following at baseline:

- Child has at least one carious lesion into dentine
- Aged ≥3 years and <8 years at the time of randomisation
- Child is receiving NHS dental care
- The intervention can be received in a comprehensible way by the child's parent/primary caregiver
- Written and informed consent obtained from child's parent/primary caregiver and agreement to comply with the requirements of the study

# 8.2 **Exclusion Criteria**

Any patient meeting any of the criteria listed below at baseline will be excluded from study participation:

- Child presents with advanced caries that require referral for extractions
- Child presents with only arrested carious lesions into dentine in primary teeth [arrested as defined within national epidemiological criteria].
- Child is living in the same household as someone already recruited to the CHOICE Trial.

# 8.3 **Co-enrolment Guidelines**

To avoid potentially confounding issues, ideally participants should not be recruited into other trials during their participation in CHOICE. Where recruitment into another trial is considered to be appropriate and without having any detrimental effect on the CHOICE trial, this must first be discussed with the LCTC who will contact the Chief Investigator ([name]).

